PSYCHOLOGICAL TREATMENT FOR ALCOHOL-RELATED LIVER DISEASE

Universal Trial Number: U1111-1230-4489

Trial Registration: ANZCTR Registration Number: ACTRN12619000710123p

SUMMARY

This project is primarily a quality assurance activity intended to determine non-inferiority or superiority of a new treatment protocol for patients with Alcoholic Hepatitis (AH) referred to the Alcohol and Drug Assessment Unit by the Department of Gastroenterology and Hepatology. In addition, we seek to collect saliva samples from these patients to replicate recent research which has identified an association between PNPLA3 gene and AH. Early evidence suggests that the risk of AH is doubled among G allele carriers of PNPLA3 (Liangpunsakul et al. 2016).

PROJECT TEAM ROLES & RESPONSIBILITIES

PROJECT TEAM SUMMARY

	Name	Health Profession	Organisation
PI	[name]	Allied Health	MSH
CI1	[name]	Medical	MSH
CI2	A/[name]	Medical	MSH
CI3	[name]	Allied Health	MSH
CI4	[name]	Medical	MSH
AI1	A/[name]	Medical	MSH
AI1	[name]	Allied Health	MSH

PROF [name] (PI)

Position:	Senior Visiting Clinical Psychologist
Organisational department:	Alcohol and Drug Assessment Unit, Division of Medicine, PAH
Phone number(s):	Primary: [name], Secondary: [name]
Email address:	[contact]
Academic Qualifications:	BA, BSocSci(Hons), PhD, FAPS, FCCLP, FCHP
Academic Appointments:	Director, Centre for Youth Substance Abuse Research, The University of Queensland Professor, Discipline of Psychiatry, The University of Queensland

Project Responsibilities: Overall project coordination.
Clinical supervision of the psychological interventions.
Ethics applications.

DR [name] (CI)

Position: Staff Specialist (Hepatologists/Gastroenterologist) and NHMRC Fellow

Organisational department: Department of Gastroenterology and Hepatology, PAH

Phone number(s): Primary: [contact]

Email address: [contact]

Academic Qualifications: Bachelor of Arts
Master of Natural Resources and Environment Agricultural Economics
Bachelor of Medicine, Bachelor of Surgery with 1st Class Honours
Fellow, RACP
Master of Public Health and Tropical Medicine
Doctor of Philosophy

Academic Appointments: Senior Lecturer at The University of Queensland
NHMRC Fellow

Project Responsibilities: Direct medical management of patients.

DR [name] (CI)

Position: Visiting Clinical Psychologist

Organisational department: Alcohol and Drug Assessment Unit, PAH

- Oragene saliva collection kits.
- Research Manager/Clinical Psychologist to coordinate the project under supervision of PI/CIs, treat all of the AH patients with tailored CBT, establish and manage databases, input clinical data, draft ethics applications, run statistical analyses and assist in preparation of research manuscript.

FUNDING/SUPPORT BEING SOUGHT OR SECURED

Secured 2019 Metro South Health Research Support Scheme Project Grant for the study entitled “When Drugs Don’t Work: Tailored Behavioural Intervention for Alcoholic Hepatitis” (2019-2020). The grant is funded by the Metro South Study, Education and Research Trust Account (SERTA).

BACKGROUND

OVERVIEW

Alcoholic hepatitis (AH) poses a significant burden on public tertiary hospitals. Medication for AH has recently been demonstrated to be ineffective in a large high-quality study. Sustained alcohol abstinence is the strongest predictor of long-term survival. Behavioural interventions to promote abstinence in AH have not been systematically assessed. We propose to trial an early and intense Cognitive Behavioural Therapy (CBT) program for patients at high risk of poor outcome of alcohol-related liver disease/severe AH and evaluate treatment outcome as a matter of quality assurance.

REVIEW AND RATIONALE

Three-month mortality from AH is 30%, with over half of AH patients dead within a year (Thursz, et al. 2015; Torok, 2015). Although specialist society guidelines recommend glucocorticoids (prednisolone) and/or nonselective phosphodiesterase inhibitors (pentoxifylline) in appropriate patients (Euro. Liver, 2012; O’Shea, et al., 2010), a recent high quality, multi-centre, double blind randomised controlled trial (RCT) published in the New England Journal of Medicine showed no benefit from prednisolone or pentoxifylline (Thursz, et al., 2015). No new pharmacological agents are imminent (Saber et al., 2016).

Abstinence is the only independent predictor of survival in AH (Potts et al. 2013). No research on behavioural approaches for AH patients to maintain alcohol abstinence is available. An effective, scalable, geographically unrestricted, cost-effective intervention is urgently required.

Meta-analyses report CBT is effective in achieving alcohol abstinence for about 25% of alcohol dependent patients ([name], et al., 2016, Lancet). Approximately half (45%) of AH patients referred to ADAU withdraw prior to commencing treatment. AH patients represent a more medically unwell group, often with established alcohol dependence, and typically featuring neuro-psychiatric and nutritional deficits of alcohol-related disease, in addition to liver failure. AH patients admitted to the PAH report an average 150g of alcohol (15 standard drinks) on each drinking occasion. Their mean WHO Alcohol Use Disorders Identification Test score is 29 (range 0-40), where > 20 indicates severe alcohol dependence. Effective early intervention and more intensive ongoing management and retention strategies are essential for this population group. A tailored CBT intervention targeting unique components of the AH disease process, psychological sequelae, and treatment accessibility is critical. No such intervention has been empirically evaluated.

The research team has significant experience in developing behavioural interventions for alcohol dependence (Young, [name], [name], 2011; [name] NHMRC APP1031909, APP455926; APP553059; [name], [name] APP1099400). There is evidence that more frequent, brief behavioural interventions are more effective than longer, less frequent appointments (O’Donnell et al. 2014). A further treatment compliance challenge is mode of delivery. AH patients are often too medically unwell to attend clinics and therefore traditional face-to-face

appointments are difficult to achieve. Critical to a tailored CBT AH intervention is a simple approach allowing flexibility in adoption across the inpatient and outpatient environments, that is cost-effective, scalable and effective. These novel efficacy data have the capacity to inform a large multi-site RCT NHMRC application.

Only a minority of heavy alcohol users develop significant liver disease. Genetic susceptibility likely contributes (Yeluru et al. 2016). The PNPLA3 gene has been reliably associated with non-alcoholic steatohepatitis and hepatitis C induced steatohepatitis (meta-analyses Chamorro et al. 2014; [name], PhD thesis). Recently, the risk (G) allele for PNPLA3 has been associated with AH, with almost double the risk for G allele carriers (Liangpunsakul et al. 2016). Existing studies characterising AH poorly identify alcohol exposure and fail to comprehensively incorporate known or suspected etiological and prognostic factors. Replication and development of this research will inform understanding of risk, treatment prognosis, and tailored behavioural treatment for AH.

AIMS

1. Examine non-inferiority or superiority of a new treatment protocol for patients with Alcoholic Hepatitis (AH) referred to the Alcohol and Drug Assessment Unit by the Department of Gastroenterology and Hepatology.
2. Replicate recent research which has found risk of AH among G allele carriers of PNPLA3.

HYPOTHESES / EXPECTED OUTCOMES

1. We expect that AH patients treated with an updated treatment protocol will have superior outcomes to historical controls of AH patients (Treatment as Usual, TAU).
 - The primary outcome will be treatment engagement and retention.
 - Secondary outcomes will include treatment initiation and drinking behaviours over treatment.
2. Genetic data will better characterize alcohol dependent patients that develop AH, compared to those that do not. The proportion of patients with risk (G) allele for PNPLA3 will be significantly higher among patients with alcoholic hepatitis than historical controls without liver disease.

PROJECT DESIGN

RESEARCH PROJECT SETTING

The research site will be based at the PAH Alcohol and Drug and Alcohol Assessment Unit (ADAU) in the Division of Medicine and Department of Gastroenterology & Hepatology (Dept. G&H).

PARTICIPANTS

RECRUITMENT

Patients are referred to the Dept. G&H for AH from the PAH Emergency Department, other medical/surgical units from other hospitals within and beyond the Metro-South District. Approximately one per week is managed for AH. All consenting patients will be offered the AH CBT program (see Procedure) and comprehensive assessment (see Measures).

ELIGIBILITY CRITERIA

All PAH AH patients will be diagnosed and medically managed by liver disease specialists (Hepatologists CI [name] and CI [name]) and Addiction specialist (CI [name]). Liver biopsy remains the gold standard for diagnosis ([name], et al., 2011), however indications for physician practice varies. While biopsy is the preferred inclusion criterion, absence will not be an exclusion criterion. For patients without liver biopsy, inclusion requires 1). Consistent alcohol risk history, 2). Absence of other acute liver injury risk; 3) at least 2/3 of:

jaundice < 8 weeks, AST/ALT ratio > 2; neutrophilia. Further characterised on AH severity (Maddrey Discriminant Function 32) and the presence of cirrhosis.

SAMPLE SIZE AND STATISTICAL OR POWER ISSUES

To determine non-inferiority or superiority of the new treatment protocol when the primary outcome is patient retention non-inferiority requirements were calculated in R version 3.5.0. Holding power level at 80% and alpha at 0.05, with a present response rate for patients with AH completing treatment at 30% and a modest protocol goal of 40%, a sample size of 70 patients is required to support non-inferiority within a 10% equivalence margin. Given that we have historical data for $N \sim 130$ patients, we only require 35 ($70 / 2 = 35$) patients to commence the new protocol for this study to be sufficiently powered.

METHODOLOGICAL APPROACH

AIM 1: ASSESSMENT OF TREATMENT PROTOCOL

Tailored CBT Intervention: Shepard et al. (2016) demonstrate that adjunctive telephone-based therapy is a cost-effective modality with good long-term treatment outcomes. As noted, it also meets all of the requirements for a medically unwell, and frequently socially, geographically or mobility challenged AH population. Critical to AH patient abstinence is development of drinking refusal self-efficacy skills, alternative coping strategies, non-pharmacological pain management, modification of situational triggers, nutrition, psychoeducation and management of alcohol craving. The Tailored Alcoholic Hepatitis Intervention will match for the existing generic face-to-face CBT Intervention historical benchmark for length of treatment (3 months) and therapist contact (8 hours). The generic alcohol CBT program has ADAU physician consult plus 8 x 1 hour face-to-face outpatient sessions over 3 months with a clinical psychologist. The Tailored Alcoholic Hepatitis intervention will have a rapid inpatient assessment to enhance treatment engagement consisting of 2 x 20 min sessions while an inpatient, including 1) ADAU Physician assessment and 2) Clinical Psychologist treatment plan. Post discharge, the same clinical psychologist will deliver the intense 2 x weekly 20 min 'booster' telephone sessions for 3 months (totaling 8 hours). Where feasible- based on patient health and geographical location- face-to-face sessions are preferred and can be substituted for telephone sessions.

AIM 2: ASSESSING GENETIC SUSCEPTABILITY TO AH.

We will genotype PNPLA3 in AH patients via saliva sample in the current study. Saliva will be collected from patients via self-collection kit. Patient's spit approximately 2ml saliva into a funnel. Saliva is mixed with a stabilization solution making it suitable for storage. The ADAU maintains a genetically informed database of > 250 treatment seeking, alcohol dependent patients without AH, who will act as our alcohol-exposure adjusted control. Ethics approval for collection and analysis of genetic data of patients attending ADAU has previously been obtained (HREC/14/QPAH/664).

ASSESSMENT AND MEASURES

Assessments are embedded within ADAU routine protocol. They are outlined below:

Assessment of alcohol use and dependence severity include the following comprehensively validated self-report measures: Brief Michigan Alcoholism Screening Test (bMAST), Alcohol Use Disorders Identification Test (AUDIT), Timeline Follow-back Procedure (TLFB), Severity of Alcohol Dependence Questionnaire (SADQ), and the Mini Alcohol Craving Experience scale (MACE). Alcohol related psychological constructs are assessed by the Drinking Expectancy Profile (DEP; outcome expectancies and refusal self-efficacy), Motivation Thought Frequency Scale (MTF; abstinence motivation), and Dysfunctional Impulsivity Scale (DIS). Social factors are examined by the Perceived Support Scale and routine assessment of demographic information. Liver disease severity will determined by MELD score. Neurocognitive functioning are assessed by the Trails A&B. Quality of Life are assessed by the Chronic Liver Disease Questionnaire (CLDQ), Short Form-6D, Depression Anxiety,

Stress Scale (DASS-21) and General Health Questionnaire (GHQ). Blood samples are taken for full medical work up as part of routine care.

RATIONALE FOR CHOICES OF METHOD/S (TIED TO PROJECT AIMS/OBJECTIVES)

As this is foremost a service improvement and quality assurance exercise, data collected will be compared to historical controls to ensure all patients receive the best available care.

TIMEFRAMES

Based on historical trends recruitment and treatment of the required 50 AH patients will take approximately 2-years from commencement of the study. Analysis of the available data and any publication is expected to be completed within 2-years following patient intervention.

PATIENT CONSENT

In standard care each patient signs a consent form agreeing that "I understand that deidentified data (anonymous data) collected may be used for program evaluation" as well as consent to participate in the program. Consistent with recent National Statement on Ethical Conduct in Human Research updates we include an 'opt-out' option at multiple points of the program.

Regarding the updated protocol and collection of genetic material, patients are verbally informed of the protocols and purpose surrounding saliva collection and provided an information sheet and consent form specifically outlining this information (attached). Patients are provided time to read the consent form and invited to ask any questions. Patients may provide or withdraw consent at any time. Provision of consent does not alter patient care in any way.

We include an additional consent provision for DNA to be available for up to 15 years and further research must be first approved by ethics committee. Patients can choose not to consent to this option. Consents will be obtained by [name] (Project manager and treating psychologist).

DATA MANAGEMENT

All data will be kept on secure, password protected, Queensland Health servers. Further access to the specific drive requires Metro South Health administration permissions and approval from the head of this department. Data will be kept consistent with ADAU (and Queensland Health) clinical guidelines, but not less than 7 years. Data used in research will be re-identifiable (coded). The coding "key" will be a password protected excel document stored within the same drive. Management practices will conform to ADAU (and Queensland Health) clinical guidelines, but not less than 7 years. Data will be destroyed via deletion of deidentified electronic file when required. Access to this deidentified data will only be granted to people approved under this application or extension to this application.

Saliva and extracted DNA samples will be stored in a locked freezer in a secure PC2 laboratory at the Queensland University of Technology (QUT). All samples will be de-identified. Laboratory protocol ensures samples are checked for viability routinely. Should a participant withdraw their consent after provision of the saliva sample their sample will be destroyed as per protocol of the PC2 laboratory at the QUT. Any electronic data generated from their sample will be deleted.

DATA ANALYSIS

Aim 1: The primary outcome will be assessed via logistic regression, where the outcome is completed treatment (0 = no, 1 = yes) and the independent variable is treatment group (0 = old protocol, 1 = new protocol). Potential confounding variables will be included as covariates (e.g. dependence severity). As the mechanism of the PNPLA3 gene is unknown it will be included as a covariate. Depending on the distribution of the number of sessions attended, parametric or non-parametric statistics may be employed to determine whether more sessions were attended on average. Again, potential confounding variables will be included as covariates.

Analysis of secondary outcomes (drinking behaviour) will be analysed using non-parametric longitudinal mixed effects models (Multilevel Modelling). LME models are considered the gold standard in psychotherapy research as they have the advantage of modelling the trajectory of longitudinal outcomes. Missing data may therefore be imputed based on individual trajectories. See above for power analysis.

Aim 2: The primary outcome will be assessed via logistic regression, where the outcome is completed G Allele of PNPLA3 (0 = no, 1 = yes) and the independent variable is AH status (0 = control, 1 = AH). Potential confounding variables will be included as covariates (e.g. dependence severity).

ANTICIPATED RISKS AND BENEFITS

The primary concern for studies utilising historical controls is that the active condition may cause harm. Given that the active condition in this study is the addition of psychological support via enhanced personalised care, no adverse effects are expected. In contrast we expect improved therapeutic outcomes, reduced social costs, and improved patient quality of life as a result of this study.

RESULTS, OUTCOMES AND FUTURE PLANS

PLANS FOR RETURN OF RESULTS OF RESEARCH TO PARTICIPANTS

Patients will be provided the results of their psychometric assessments and blood tests as a matter of routine care. As outcomes from genetic data is not clinically meaningful the results will not be fed back to patients. Research outcomes will be made available to participants upon request; in which case a research summary will be emailed to patients upon completion.

PLANS FOR DISSEMINATION AND PUBLICATION OF PROJECT OUTCOMES

Summary statistics (e.g. descriptive and inferential statistics) of deidentified data are intended to be published within peer reviewed journals and may be presented at academic conferences. The outcomes of this study may also provide grounds for future grant applications to fund more robust clinical RCTs.

OTHER POTENTIAL USES OF THE DATA AT THE END OF THE PROJECT

Any further use of the data collected will be requested via ethics application. The most likely use is for identification of prognostic markers and intervention targets as a matter of quality assurance, program evaluation, and program development.

REFERENCES

- [name], JP, et al., 2016. Alcohol use disorders. *The Lancet* 387:988-998.

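### Drinking over treatment is naturally compared among patients who start, but starting is an outcome the new protocol is meant to raise, so the comparison can be biased in either direction by who starts

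*Protocol*

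**What the plan says.** Under Hypotheses / Expected Outcomes, the Protocol expects a benefit in treated patients: "We expect that AH patients treated with an updated treatment protocol will have superior outcomes to historical controls of AH patients". Initiation and drinking then stand side by side as secondary outcomes: "Secondary outcomes will include treatment initiation and drinking behaviours over treatment". Review and Rationale gives the historical loss before the first session: "Approximately half (45%) of AH patients referred to ADAU withdraw prior to commencing treatment". The section on Aim 1 under Methodological Approach says the new intervention "will have a rapid inpatient assessment to enhance treatment engagement", whereas the generic programme's psychologist sessions are outpatient visits. Sample Size counts 35 "patients to commence the new protocol for this study to be sufficiently powered". Data Analysis plans longitudinal mixed models for drinking, chosen for "the advantage of modelling the trajectory of longitudinal outcomes", with missing values imputed from each individual's own trajectory.

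The document does not say whether never-starters enter the drinking comparison. It names no drinking measure for them and no adjustment of the drinking analysis for a difference in initiation.

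**The concern.** A patient who never starts has no on-treatment drinking record, so imputation along individual trajectories has nothing to work from. On the natural reading, the drinking model therefore holds starters only. Starting happens after referral, and the new protocol sets out to change it. If it succeeds, the new group's starters include patients who under the old programme would have been among the 45% lost. The two sets of starters then differ in make-up, and a drinking difference mixes that selection with any effect of treatment. Full follow-up of every starter and an identical starting rule in both periods would not remove this.

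At stake is the reading of the drinking result. Review and Rationale treats abstinence as the key to survival and expects these data to support an application for a larger randomised trial. An apparent deficit or an apparent gain could each be misread as an effect of the programme.

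**Working it through.** **Plan's own figure.** There is none for drinking. The only calculated figure, 70, is for completion: (1.645 + 0.842)² × (0.30×0.70 + 0.40×0.60) / (0.10 + 0.10)² = 69.6, so 70 per group at one-sided 5%. It has no part in what follows.

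**Inputs.**
- Old start rate: 1 − 0.45 = 0.55 (Review and Rationale).
- Abstinence 25%: the same section says "CBT is effective in achieving alcohol abstinence for about 25% of alcohol dependent patients". That is not a figure for AH patients, and applying it here is an assumption.
- New start rate *s*, and abstinence *p* among the extra starters: not in the documents, so assumed and varied.
- Neither programme changes anyone's drinking.

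**Check 1: mixing.** Patients who would start anyway are 25% abstinent in both periods. Starters-only abstinence in the new group is (0.55×0.25 + (s − 0.55)×p) / s. For s = 0.75 and p = 0.10 this is (0.1375 + 0.0200) / 0.75 = 21.0%, against 25.0% in the old group. Differences from the old group, in points:

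| s | p = 0% | p = 5% | p = 10% | p = 15% | p = 25% | p = 35% |
|---|---|---|---|---|---|---|
| 0.65 | −3.8 | −3.1 | −2.3 | −1.5 | 0 | +1.5 |
| 0.75 | −6.7 | −5.3 | −4.0 | −2.7 | 0 | +2.7 |
| 0.85 | −8.8 | −7.1 | −5.3 | −3.5 | 0 | +3.5 |

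The sign depends only on whether *p* lies below or above 25%. If drinking were observed in everyone referred, with p = 10%, both groups would show 0.1375 + 0.45×0.10 = 18.25%.

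**Check 2: a common cause.** Let a normally distributed motivation score *M* drive both starting and abstinence: P(abstinent) = expit(a + bM), set to 25% overall, and P(start) = expit(c + dM), or a cut-off on *M*, set to the start rate. Abstinence among starters:

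| Link | 55% start | 80% start | 100% start |
|---|---|---|---|
| weak (b = d = 0.5) | 26.9% | 25.8% | 25.0% |
| moderate (b = d = 1) | 30.9% | 27.5% | 25.0% |
| strong (b = 1.5, cut-off) | 39.8% | 30.5% | 25.0% |

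The apparent deficit at 80% starting is 1.1, 3.4 or 9.3 points.

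**Check 3: the obvious replacement.** Take all referred patients as denominator and count every never-starter as drinking. The same no-effect scenarios give start rate × starters' abstinence:
- weak: 0.55×26.9 = 14.8% against 0.80×25.8 = 20.6%, a false gain of 5.8 points;
- moderate: 0.55×30.9 = 17.0% against 0.80×27.5 = 22.0%, +5.0;
- strong: 0.55×39.8 = 21.9% against 0.80×30.5 = 24.4%, +2.5.

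Giving never-starters their group's starter rate returns the Check 2 figures. In these scenarios the two results point in opposite directions, which correctly blocks a claim.

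**Limit of the pair.** With p = 35% and s = 0.75 in Check 1, the results are 25.0% against 27.7% and 13.75% against 0.75×27.67 = 20.75%. Both favour the new protocol although nothing has changed. Agreement is therefore necessary for a claim but does not prove one.

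**The case against.** The strongest objection is that the denominator is inferred. Drinking over treatment could mean the 3-month window, Aim 1 speaks of referred patients, all consenting patients are to be offered assessment, and a SAP that is not shown could fix the population. It stands that no passage says starters only. It does not dispose of the point: the wording on treated patients, on drinking over treatment and on commencing all leads to starters, and the planned trajectory imputation cannot bring back patients without a trajectory.

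A reader might infer that success on initiation must make drinking look worse, because the extra starters are the less motivated. The documents do not support that. They attribute no share of the 45% to low motivation, and they name illness, distance, mobility and social difficulty as barriers, which inpatient and telephone contact addresses. Only a conditional statement holds.

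The sizes are also open to challenge. The 9-point figure needs a strict cut-off on motivation. The checks use abstinence at one time, while the plan has a trajectory model in which a stable difference between patients would enter the level rather than the slope; the effect on that model was not computed. With 35 new patients and 130 historical ones, the standard error of a difference around 25% is √(0.25×0.75×(1/35 + 1/130)) = 8.2 points, about as large as most of these biases. All of this stands and limits the figures to illustration.

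Finally, Assessment and Measures includes abstinence motivation and dependence severity, so covariate adjustment is possible. Data Analysis mentions it for completion and for session counts but not for drinking. It could reduce selection among starters on those measures, but would not supply outcomes for never-starters.

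**Conclusion.** The point holds in conditional form. On the natural reading, the drinking comparison is made among starters, and starting is something the new protocol is designed to raise from about 55%. The comparison can therefore be biased by who starts. The direction depends on whether the extra starters drink more or less than those who would have started anyway. The size is illustrative: about 1 to 9 points against the new protocol at 80% starting in the motivation scenarios, and 2.7 points in its favour at 75% starting if the extra starters are 35% abstinent. It rests on the inferred denominator, on 25% abstinence borrowed from alcohol-dependent patients generally, and on assumed start rates and links. It concerns a secondary outcome in a historical-control study. It does not show that an adverse result is to be expected or that a true benefit would be understated.

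**What to change.** In Hypotheses / Expected Outcomes and in Data Analysis:

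1. State that the mixed-model drinking comparison is conditional on starting and is descriptive, and that no superiority or inferiority conclusion on drinking will be drawn from it alone.
2. Beside it, report 3-month abstinence with all AH patients referred in each period as denominator, always as two sensitivity results: never-starters all counted as drinking, and never-starters at their own group's starter rate.
3. Claim a drinking difference only if both agree in direction, and say that the pair does not cover never-starters who do better than starters.
4. Do not make the proportion recorded abstinent the single main result, because it favours whichever group has more starters.
5. State how deaths before 3 months are counted, since Review and Rationale puts 3-month mortality from AH at 30%.

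The referral denominator is already needed for the initiation outcome, and the 45% implies that it exists for the historical period. The cost is wording and one extra tabulation. The downside is a wider and less favourable drinking statement.

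### The power statement is offered for non-inferiority or superiority, but only non-inferiority was calculated; superiority power is about 19–25% at two-sided 0.05

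*Protocol*

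**What the plan says.** Aim 1 of the Protocol names both non-inferiority and superiority. Under Hypotheses / Expected Outcomes only one direction is given: patients on the updated protocol "will have superior outcomes to historical controls of AH patients", with engagement and retention as the primary outcome.

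The section Sample Size and Statistical or Power Issues gives this purpose: "To determine non-inferiority or superiority of the new treatment protocol when the primary outcome is patient retention non-inferiority requirements were calculated". Its inputs are "Holding power level at 80% and alpha at 0.05", 30% completion now and a goal of 40%. Its result is that "a sample size of 70 patients is required to support non-inferiority within a 10% equivalence margin". Because "we have historical data for $N \sim 130$ patients", it halves 70 to 35 new patients and concludes that power is sufficient. The Timeframes section, however, gives the required number as 50.

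Under Data Analysis, the primary outcome is a logistic regression of completion on treatment group, with covariates; no margin is mentioned there. The paragraph on drinking outcomes closes with "See above for power analysis". The Protocol gives no power or sample size for superiority.

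**The concern.** A sentence that sets out to serve two objectives is followed by a calculation for one of them, and then by an unqualified statement of adequate power. The objective left out is the one stated as the hypothesis. It is also the natural reading of a group coefficient tested without a margin.

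The two objectives differ greatly in difficulty here. The non-inferiority calculation adds the hoped-for 10-point gain to the 10-point margin, so it has 20 points to work with. Superiority has only the 10-point gain. If superiority power is low, a program that meets its 40% goal exactly would still usually miss significance, in a study described as adequately powered. That matters because the Protocol intends the data to inform a later multi-site trial application.

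**Working it through.** **Inputs (all from the Protocol).** Historical completion 30%, new-protocol goal 40%, margin 10 points, alpha 0.05 (sidedness not stated), target power 80%, about 130 historical controls, and new patients 35 (sample-size section) or 50 (Timeframes). Variance terms: 0.30 × 0.70 = 0.21 and 0.40 × 0.60 = 0.24.

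**1. Reproducing the stated 70.** n per arm = (z_alpha + z_power)² × (0.21 + 0.24) / (0.40 − 0.30 + 0.10)².
- One-sided 0.05: (1.645 + 0.842)² × 0.45 / 0.20² = 69.6, so 70.
- One-sided 0.025: 89.

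So 70 is a per-arm non-inferiority figure at one-sided 0.05.

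**2. Superiority power, 40% versus 30%, 130 controls.** Power = Φ(0.10/SE − z), with SE = √(0.24/n + 0.21/130).
- n = 35: SE = √(0.00686 + 0.00162) = 0.0920. Two-sided 0.05: Φ(1.086 − 1.960) = 19.1%. One-sided 0.05: Φ(1.086 − 1.645) = 28.8%.
- n = 50: SE = √(0.00480 + 0.00162) = 0.0801. Two-sided: Φ(1.248 − 1.960) = 23.8%. One-sided: Φ(1.248 − 1.645) = 34.6%.

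Other standard tests change little:

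| Method | 35 new, two-sided | 50 new, two-sided | 35 new, one-sided | 50 new, one-sided |
|---|---|---|---|---|
| Unpooled difference | 19.1% | 23.8% | 28.8% | 34.6% |
| Log odds ratio (Wald) | 20.0% | 24.7% | 30.0% | 35.6% |
| Pooled z, approximation | 21.0% | 25.4% | 30.8% | 36.1% |
| Pooled z, exact enumeration | 21.1% | 25.1% | 30.8% | 36.0% |

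**3. Ceiling with 130 controls.** As the new group grows without limit, SE falls only to √(0.21/130) = 0.0402. Two-sided 0.05: Φ(0.10/0.0402 − 1.960) = 70.1% (pooled 65.3%, log odds ratio 63.6%). By the unpooled formula, even an unlimited new group would need 0.21 × (1.960 + 0.842)² / 0.10² ≈ 165 controls for 80%. A 1:1 superiority design needs 356 per arm (two-sided, pooled formula).

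**4. Detectable difference at 80% power (two-sided, pooled, 130 controls).** New-protocol completion would have to be about 56% with 35 patients or 53% with 50: gains of roughly 26 and 23 points, against a goal of 10.

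**5. Non-inferiority power, one-sided 0.05, 10-point margin, 130 controls.**
- True 40% versus 30%: n = 35, Φ(0.20/0.0920 − 1.645) = 70%; n = 50, Φ(0.20/0.0801 − 1.645) = 80%. At one-sided 0.025 these are 58% and 70%.
- True 30% in both: n = 35, Φ(0.10/√(0.21/35 + 0.21/130) − 1.645) = 31%; n = 50, 37%.

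None of these figures allows for covariate adjustment or for bias in the historical comparison.

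**The case against.** The sample-size section says openly that non-inferiority requirements were calculated and that 70 supports non-inferiority. The closing claim of adequate power can therefore be read as belonging to that calculation alone. This stands in part: no superiority calculation was made, so none was made wrongly. The fault is that the stated purpose includes superiority and the hypothesis is superiority, while the power claim is not limited to the objective it covers.

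The Protocol does not state sidedness, and its 70 points to one-sided 0.05. This stands, so both conventions are shown. Superiority power remains far below 80% under either.

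Four stronger readings are tempting, and the documents do not support them:
- A reader might infer that 80% superiority power is impossible at any enrolment under any test. That is strict only at two-sided 0.05. At one-sided 0.05 the unpooled ceiling is 80.0%, first reached near 116,000 new patients; the exception has no practical use, but it exists.
- A reader might infer that assuming a benefit in a non-inferiority calculation is an error. It is permissible when disclosed, and the Protocol discloses both 30% and 40%. Power at equal completion is a useful sensitivity figure, not a correction.
- A reader might infer that the stated 80% is at least right for non-inferiority. At 35 new patients it is about 70%; it holds only at 50, and at one-sided 0.05.
- A reader might infer that the investigators would take a null superiority result as evidence against the program. The Protocol does not say so, and it describes the work chiefly as service improvement and quality assurance. The risk of misreading is real, but it is not a stated plan.

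The cross-reference after the drinking outcomes is a minor point. It may be meant for Aim 1 as a whole, but where it stands it attaches a binary-completion calculation to longitudinal drinking data.

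**Conclusion.** The concern holds. The power claim is offered for two objectives and supported for one, and the unsupported one is the hypothesis. Superiority power is about 19–21% with 35 new patients and 24–25% with 50 at two-sided 0.05, or 29–31% and 35–36% at one-sided 0.05. At two-sided 0.05 the ceiling with 130 controls is about 64–70%. The non-inferiority claim itself reaches 80% only with 50 new patients, at one-sided 0.05 and if the 40% goal is truly met.

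These results rest on the Protocol's own rates, on 130 usable controls, and on an unadjusted comparison.

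**What to change.** - **Sample-size section:** state the sidedness of alpha and remove superiority from the power claim. Say that the calculation covers only non-inferiority with a 10-point margin under a true 40% versus 30%, with power of about 70% at 35 new patients and 80% at 50 (one-sided 0.05, 130 controls). Reconcile 35 with the 50 under Timeframes. Report superiority power (about 19% at 35 and 24% at 50, two-sided) and, as a sensitivity figure, non-inferiority power at equal completion (31% and 37%).
- **Hypotheses and Data Analysis:** make non-inferiority against the 10-point margin, on the risk-difference scale, the confirmatory test. Test superiority only after it, and report it as an estimate with its confidence interval.
- **Secondary-outcome paragraph:** delete the reference back to the power analysis, or limit it to the completion outcome.

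The edits are short, but ordering the two tests changes the test structure as well as the wording. The stated power becomes less favourable and the confirmatory claim narrower. If 50 is confirmed as the target, recruitment stays as the Timeframes section has it.
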